6.1.1 Additional study treatments

No other treatment beyond investigational drug and control drug are included in this trial.

6.1.2 Treatment arms/group

At baseline, all participants will be randomized 1:1 to one of the two treatment groups:

- **Inclisiran Group:** 100 participants. Treated with inclisiran sodium 300mg s.c. on Day 1, Day 90 and Day 270, and with matching placebo s.c. on Day 180.
- **Control Group:** 100 participants. Treated with matching placebo s.c. on Day 1 and Day 90, and with inclisiran sodium 300mg on Day 180 and Day 270.

Subcutaneous injections of the Inclisiran/placebo will not be dispensed to the participants but rather administered by qualified personnel at the study site on Day 1, Day 90, Day 180 and Day 270.

6.1.3 Treatment duration

The expected duration of the participant's involvement in the study will be approximately 374 days, which includes a screening period (14 days), a subsequent 180-day double-blind, placebo-controlled treatment period (core part), and a 180-day open label treatment period (extension part).

Participants may be discontinued from the study treatment earlier due to any reasons, at the discretion of the investigator or the participant. They will continue to be followed up in the study until EOS as per Assessment Schedule ([Table 1-2](#)).

6.2 Preparation, handling, storage, and accountability

Each study site will be supplied with study treatment in packaging as described under [Table 6-1](#) Investigational and control drugs section. A unique medication number is printed on the study medication label.

Investigator staff will identify the study medication kits to administer to the participant by contacting the IRT and obtaining the medication number(s). The study medication has a 2-part label (base plus tear-off label), immediately before dispensing the medication kit to the participant, site personnel will detach the outer part of the label from the packaging and affix it to the source document.

6.2.1 Handling of study treatment

Study treatment must be received by a designated person at the study site, handled and stored safely and properly and kept in a secured location to which only the Investigator and designated site personnel have access. Upon receipt, all study treatment must be stored according to the instructions specified on the labels

Clinical supplies are to be dispensed only in accordance with the protocol. Technical complaints are to be reported to the respective Novartis Country Organization Quality Assurance.

Medication labels will be in the local language and comply with the legal requirements. They will include storage conditions for the study treatment but no information about the participant except for the medication number.

The Investigator or designated site staff must maintain an accurate record of the shipment and dispensing of study treatment in a drug accountability log. Monitoring of drug accountability will be performed by field monitors during site or remote monitoring visits, and at the completion of the trial.

The site may destroy and document destruction of unused study treatment, drug labels and packaging, as appropriate in compliance with site processes, monitoring processes, and per local regulation/guidelines. Otherwise, the Investigator will return all unused study treatment, packaging, drug labels, and a copy of the completed drug accountability log to the Novartis monitor or to the Novartis address provided in the Investigator folder at each site.

6.2.2 Handling of other treatment

Not applicable

6.2.3 Instruction for prescribing and taking study treatment

Blinded s.c. injections of inclisiran/placebo, will not be dispensed to the participants, but will be administered by qualified personnel at the study site.

The preferred site of injection is the abdomen. Alternative injection sites include the upper arm or thigh. Injections should not be made into areas of active skin disease or injury such as sunburns, skin rashes, inflammation, tattoos, or skin infections.

Participants will be administered an injection of blinded s.c. inclisiran/placebo on Day 1, Day 90, Day 180 and Day 270 as specified in the Assessment Schedule ([Table 1-2](#)) after all other study assessments have been completed for the visit.

Table 6-2 Dose and treatment schedule

Investigational / Control Drug (Name and Strength)	Dose	Frequency and/or Regimen
Inclisiran sodium 300 mg (equivalent to 284 mg inclisiran*)	300 mg	Day 1, Day 90, Day 180 and Day 270
matching s.c. placebo	0 mg	Day 1, Day 90 and Day 180

* also known as KJX839

All kits of study treatment assigned by the IRT will be recorded in the IRT system. All injections of inclisiran/placebo given to the participant as well as study drug interruptions/discontinuations (i.e., no injection at a designated dosing visit) during the study must be recorded on an appropriate eCRF and within IRT.

6.3 Measures to minimize bias: randomization and blinding

6.3.1 Treatment assignment, randomization

At baseline visit (Day 1) , all eligible participants will be randomized via Interactive Response Technology (IRT) to one of the treatment arms. The Investigator or his/her delegate will contact the IRT after confirming that the participant fulfills all the inclusion/exclusion criteria. The IRT will assign a randomization number to the participant, which will be used to link the participant to a treatment arm and will specify a unique medication number for the first package of study treatment to be dispensed to the participant.

The randomization numbers will be generated using the following procedure to ensure that treatment assignment is unbiased and concealed from participants and Investigator staff. A participant randomization list will be produced by the IRT provider using a validated system that automates the random assignment of participant numbers to randomization numbers. These randomization numbers are linked to the different treatment arms, which in turn are linked to medication numbers. A separate medication list will be produced by or under the responsibility of Novartis Global Clinical Supply (GCS) using a validated system that automates the random assignment of medication numbers to packs containing the study treatment.

The randomization scheme for participants will be reviewed and approved by a member of the Randomization Office.

6.3.2 Treatment blinding

Participants, Investigator, site staff, persons performing the assessments, monitors and the Novartis CTT will remain blinded to the identity of the treatment throughout the core part after randomization. Participants, investigators and site staff should continue to remain blinded throughout the study until final database lock.

Unblinding a single participant at site for safety reasons (necessary for participant management) will occur via an emergency system in place at the site. As a result, the participant should be discontinued from the study treatment.

The following methods will be used to maintain the blind:

- (1) Randomization data will be kept strictly confidential until the time of final database lock.
- (2) the identity of the treatments will be concealed by the use of study treatment that are all identical in packaging, labeling, schedule of administration, appearance, taste, and odor.
- (3) data with unblinding potential, such as lipid results and PCSK9 results collected after the screening visit, will be kept blind until the time of final database lock.

6.3.3 Emergency breaking of assigned treatment code

Emergency code breaks must only be undertaken when it is required to in order to treat the participant safely.

Most often, discontinuation from study treatment and knowledge of the possible treatment assignments are sufficient to treat a study participant who presents with an emergency condition. Emergency treatment code breaks are performed using the IRT. When the Investigator contacts the system to break a treatment code for a participant, he/she must provide the requested participant identifying information and confirm the necessity to break the treatment code for the participant. The Investigator will then receive details of the investigational drug treatment for the specified participant and a fax or email confirming this information. The system will automatically inform the Novartis monitor for the site and the study team that the code has been broken.

It is the Investigator's responsibility to ensure that there is a dependable procedure in place to allow access to the IRT/code break cards at any time in case of emergency. The Investigator will provide:

- protocol number
- participant number

In addition, oral and written information to the participant must be provided on how to contact his/her backup in cases of emergency, or when he/she is unavailable, to ensure that un-blinding can be performed at any time.

After an emergency unblinding, study treatment should be permanently discontinued. The participant will continue to be followed up in the study unless informed consent is withdrawn ([Section 7.3](#)) or until participant have completed the EOS visit as per Assessment Schedule ([Table 1-2](#))

6.4 Study treatment compliance

The treatment information must be captured in the source documents, the appropriate Case Report/Record Form (CRF) and in the Drug Accountability Log.

6.4.1 Recommended treatment of adverse events

AEs should be treated according to local practice and guidelines, and is at the discretion of the investigator and treating physician.

For participants with injection site reaction, antihistamines, local or systemic steroids can be used at the investigator's discretion depending on the severity of the reaction.

Medication used to treat adverse events (AEs) must be recorded on the appropriate CRF.

6.5 Dose modification

Investigational or other study treatment dose adjustments and/or interruptions are not permitted.

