6.7 Treatment of overdose

In the event of an overdose, the investigator/ site staff should:

- Contact the monitor immediately.
- Evaluate the participant to determine, in consultation with the monitor, whether study treatment should be interrupted or whether the dose should be reduced.
- Closely monitor the participant for any AE/SAE and laboratory abnormalities
- Document the quantity of the excess dose as well as the duration of the overdose.

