10.5.1 Liver event and laboratory trigger definitions & follow-up requirements

Table 10-1 Liver event and laboratory trigger definitions

Definition/ threshold	
Liver laboratory triggers If ALT, AST and total bilirubin normal at baseline:	
 • ALT or AST > 5 × ULN • ALP > 2 × ULN (in the absence of known bone pathology) • Total bilirubin > 3 × ULN (in the absence of known Gilbert syndrome) • ALT or AST > 3 × ULN and INR > 1.5 • Potential Hy's Law cases (defined as ALT or AST > 3 × ULN and Total bilirubin > 2 × ULN [mainly conjugated fraction] without notable increase in ALP to > 2 × ULN) • Any clinical event of jaundice (or equivalent term) • ALT or AST > 3 × ULN accompanied by (general) malaise, fatigue, abdominal pain, nausea, or vomiting, or rash with eosinophilia • Any adverse event potentially indicative of a liver toxicity
If ALT or AST abnormal at baseline:	• ALT or AST > 3x baseline or > 300 U/L (whichever occurs first)

Table 10-2 Follow up requirements for liver laboratory triggers - ALT, AST, TBL

ALT	TBL	Liver Symptoms	Action
ALT increase without bilirubin increase:			
If normal at baseline: ALT > 3 x ULN	Normal For participants with Gilbert's syndrome: No change in baseline TBL	None	
 No change to study treatment Measure ALT, AST, ALP, GGT, TBIL, INR, albumin, CK, and GLDH in 48-72 hours. Follow-up for symptoms.
If elevated at baseline: ALT > 2 x baseline or > 300 U/L (whichever occurs first)			
If normal at baseline: ALT > 5 x ULN for more than two weeks	Normal For participants with Gilbert's syndrome: No change in baseline TBL	None	
 Interrupt study treatment Measure ALT, AST, ALP, GGT, TBIL, INR, albumin, CK, and GLDH in 48-72 hours. Follow-up for symptoms. Initiate close monitoring and workup for competing etiologies. Study treatment can be restarted only if another etiology is identified and liver enzymes return to baseline.
If elevated at baseline: ALT > 3 x baseline AND >5x ULN for more than two weeks			
If normal at baseline: ALT > 8 x ULN	Normal	None	
ALT increase with bilirubin increase:			
If normal at baseline: ALT > 3 x ULN	TBL > 2 x ULN (or INR > 1.5) For participants with Gilbert's syndrome: Doubling of direct bilirubin	None	
If elevated at baseline: ALT > 2 x baseline AND >3x ULN			
If normal at baseline: ALT > 3 x ULN	Normal or elevated	Severe fatigue, nausea, vomiting, right upper quadrant pain	

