If elevated at baseline: ALT > 2 x baseline AND >3x ULN, OR ALT > 300 U/L			

Table 10-3 Follow up requirements for liver laboratory triggers - Isolated Hyperbilirubinemia

Criteria	Actions required	Follow-up monitoring
Total Bilirubin (isolated)		
>1.5 – 3.0 ULN	
 Maintain treatment Repeat LFTs within 48-72 hours 	Monitor LFTs weekly until resolution to ≤ Grade 1 or to baseline
> 3 - 10 x ULN (in the absence of known Gilbert syndrome)	
 Interrupt treatment Repeat LFT within 48-72 hours Hospitalize if clinically appropriate Establish causality Record the AE and contributing factors (e.g. conmeds, med hx, lab) in the appropriate CRF 	Monitor LFTs weekly until resolution to ≤ Grade 1 or to baseline (ALT, AST, total bilirubin, Alb, PT/INR, ALP and GGT) Test for hemolysis (e.g. reticulocytes, haptoglobin, unconjugated [indirect] bilirubin)
> 10 x ULN	
 Discontinue the study treatment immediately Hospitalize the participant Establish causality Record the AE and contributing factors (e.g. 	ALT, AST, total bilirubin, Alb, PT/INR, ALP and GGT until resolution (frequency at Investigator discretion)

Criteria	Actions required	Follow-up monitoring
Any AE potentially indicative of a liver toxicity	
conmeds, med hx, lab)in the appropriate CRF
 
• Consider study treatment interruption or discontinuation• Hospitalization if clinically appropriate• Establish causality• Record the AE and contributing factors(e.g. conmeds, med hx, lab)in the appropriate CRF	Investigator discretion

Based on Investigator's discretion investigation(s) for contributing factors for the liver event can include: Serology tests, imaging and pathology assessments, hepatologist's consultancy; obtaining more detailed history of symptoms and prior or concurrent diseases, history of concomitant drug use, exclusion of underlying liver disease.

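### Protocol Section 6.5 forbids any interruption of study treatment while the liver tables order it, leaving open whether a dose may be withheld and treatment later resumed

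*Protocol*

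**What the plan says.** Protocol Section 6.5 is a single sentence, stating for all study treatment that "dose adjustments and/or interruptions are not permitted". It names no exception and does not refer to the liver appendix. Section 6.5.2.1, on drug-induced liver injury and under the same heading, adds none.

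Other parts of the protocol provide for what 6.5 rules out:

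- **Section 10.5, general text.** After a confirmed elevation, interruption is to be considered. The appendix describes its process as one that sites must follow.
- **Table 10-2.** The action is "Interrupt study treatment", and then: "Study treatment can be restarted only if another etiology is identified and liver enzymes return to baseline".
- **Table 10-3, isolated total bilirubin > 3 - 10 x ULN.** "Interrupt treatment Repeat LFT within 48-72 hours".
- **Table 10-3, any adverse event suggesting liver toxicity.** "Consider study treatment interruption or discontinuation".
- **Section 6.7 (overdose).** The site is to evaluate, with the monitor, "whether study treatment should be interrupted or whether the dose should be reduced".
- **Section 8.6.1.** Dose reduction or increase and drug interruption appear among the possible actions for an adverse event.
- **Section 6.2.3.** An interruption is described as a dosing visit without an injection, to be recorded in the eCRF and in IRT.

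For the analysis, the primary estimand (Protocol 3.1, SAP 1.2.1) lists permanent discontinuation, prohibited lipid-lowering therapy and death as intercurrent events. Temporary interruption is not listed.

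**The concern.** Two binding instructions conflict at a moment that matters for safety: whether to inject a participant who has a liver signal. Different sites could act differently, each citing the protocol, and a site that follows the liver tables would have a deviation from 6.5. Section 8 allows no waivers or exemptions, so the conflict cannot be settled case by case.

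The statistical side is secondary. The same clinical event, a Day 90 injection withheld for a liver abnormality, may be labelled a temporary interruption at one site and a permanent discontinuation at another. Only the second label is an intercurrent event, and the imputation rules depend on it.

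**Working it through.** The documents give no figure to reproduce, so the check is mainly a comparison of texts.

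**1. Can the passages be read as consistent?**

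- *Interruption as another word for discontinuation.* This fails. Table 10-2 sets a condition for restart, and Table 10-3 has a separate row, above 10 x ULN, that orders discontinuation.
- *Interruption as an empty term for infrequent injections.* This fails, because Section 6.2.3 gives it a meaning: no injection at a dosing visit.
- *The specific rule overrides the general one.* This is reasonable drafting practice, but no text says so.

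The conflict between 6.5 and 10.5 therefore stands. In the text available, the action cells of the later rows of Table 10-2 are blank, probably because cells were merged. Which rows carry the order should be read from the original. At least one row (ALT > 5 x ULN for more than two weeks, if normal at baseline) clearly does.

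**2. Which dose can affect the primary endpoint?** The liver rules apply once a participant has been exposed, so Day 1 is out. Day 180 and Day 270 come after Day 150. That leaves Day 90. Unless the injection can still be given within the visit window (±7 days), the next scheduled dosing visit is Day 180. At Day 150 such a participant will normally not have resumed, whichever label applies.

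**3. What does the label change?**

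- *Primary analysis, Day 150 observed, no prohibited therapy.* Nothing changes for that value. Discontinuation follows treatment policy (SAP 2.5.3), and step 3 of SAP 5.4.1.1 resets a value only if it was missing and fell after discontinuation.
- *Primary analysis, Day 150 missing.* Labelled an interruption, the value is by default imputed under MAR within the arm (SAP 2.5.4). Labelled a discontinuation, it is imputed from retrieved-dropout data or, if these are insufficient, by the control-based model. In the inclisiran arm the control-based route is the less favourable to the drug.
- *On/off-treatment indicator.* The retrieved-dropout model uses treatment status at each visit. No rule classifies a participant whose dose was withheld but who has not been discontinued.
- *Supplementary analysis 1 (SAP 5.4.1.2).* Values on or after any intercurrent event are set to missing. Here the label decides whether an observed Day 150 value is kept or replaced.

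**4. Size, as an illustration.** The documents give no rate for these events. Take 100 inclisiran participants (Protocol 6.1.2) and suppose that the label moves one participant from full response to control level. For the gap, use the placebo-adjusted 57.2 points at Day 330 that Protocol 2.2 reports from the phase 3 study in Asian patients.

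Shift in arm mean = k × 57.2 / 100

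- k = 1: 0.57 points
- k = 2: 1.14 points
- k = 3: 1.72 points

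One participant is thus about 1% of the assumed effect. A full swing is a large assumption, since the imputation models condition on the participant's own earlier LDL-C values.

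**The case against.** The best case against is that nobody is endangered and the result is not at risk. Much of that stands, and it rules out several stronger readings.

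- A reader might infer that 6.5 forces sites to keep dosing through a liver signal. It does not. Section 7.1 requires discontinuation where the investigator believes that continuing would harm the participant, or judges that a laboratory abnormality prevents continuation. Section 10.1.8.1 expects immediate safety action even when it is a deviation.
- A reader might infer that discontinuation in itself sends the participant to imputation. It does not. Participants who stop treatment are asked to keep attending visits, and a measured Day 150 value enters the primary model under either label.
- Section 6.7 might be read as authorising a dose change. It asks only for an evaluation, which can end in no change. It sits awkwardly with 6.5 but does not contradict it outright.
- Both liver tables might be thought to govern restart. Only Table 10-2 does.
- It might seem that recording is unaddressed. Section 6.2.3 already requires interruptions to be entered in the eCRF and IRT.

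It can also be argued that, because discontinuation is defined as permanent (Protocol 7.1 and 10.2.2), a temporary hold is plainly not that intercurrent event. That settles the label where restart is clearly intended. It does not settle the status of a participant whose Day 90 dose was withheld and who had not resumed by Day 150, nor the on/off-treatment indicator.

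None of these points removes the clash between 6.5 and the liver tables.

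**Conclusion.** The protocol contradicts itself on whether study treatment may be interrupted: Section 6.5 against Section 10.5 and Tables 10-2 and 10-3, with looser tension from Sections 6.7 and 8.6.1. Permanent discontinuation and urgent safety action remain available, so the unresolved question is whether a dose may be temporarily withheld and treatment later resumed. That is safety-relevant and deserves correction for that reason.

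The effect on the analysis is small and conditional. For the primary endpoint it needs a withheld Day 90 dose, a missing Day 150 value and a label that could go either way. For supplementary analysis 1 it can arise with Day 150 observed. About 0.6 points per participant rests on the assumed full swing and the borrowed 57.2-point gap. The documents give no reason to expect many such participants: Protocol 2.2 reports no increased risk of hepatic dysfunction with inclisiran. Nothing here suggests that the primary conclusion would change.

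**What to change.** **Protocol.** Reconcile Sections 6.5, 6.7, 8.6.1 and 10.5 (with Tables 10-2 and 10-3) so that they give one instruction, or state which text prevails. The clinical rule is the sponsor's to choose.

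**SAP.** In Sections 2.5.3 and 5.4.1, state whether a dose withheld under the liver tables and not resumed by Day 150 counts as treatment discontinuation, and so as off-treatment, for the imputation and for supplementary analysis 1. The latest SAP amendment is dated before the final database lock. If the core database is already locked, the report should give the classification that was used and the number of participants it touched.

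**Cost.** A wording amendment to the protocol and a sentence or two in the SAP. No procedure, visit or data item is added, since interruptions are already recorded.

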6.5.1 Definitions of dose limiting toxicities (DLTs)

Not applicable.

6.5.2 Follow-up for toxicities

All participants must be followed up for adverse events and serious adverse events for 30 days following the last dose of inclisiran/placebo.

6.5.2.1 Follow up on potential drug-induced liver injury (DILI) cases

Participants with transaminase increase combined with total bilirubin increase may be indicative of potentially severe DILI and should be considered as clinically important events and assessed appropriately to establish the diagnosis. The required clinical information, as detailed below, should be sought to obtain the medical diagnosis of the most likely cause of the observed laboratory abnormalities.

The threshold for potential DILI may depend on the participant's baseline AST/ALT and total bilirubin value; participants meeting any of the following criteria will require further follow-up as outlined below:

- For participants with normal ALT and AST and total bilirubin value at baseline: AST or ALT $> 3.0 \times$ ULN combined with total bilirubin $> 2.0 \times$ ULN
- For participants with elevated AST or ALT or total bilirubin value at baseline: [AST or ALT $> 2 \times$ baseline] OR [AST or ALT $> 300 \text{ U/L}$], whichever occurs first combined with [total bilirubin $> 2 \times$ baseline AND $> 2.0 \times$ ULN]

As DILI is essentially a diagnosis of exclusion, other causes of abnormal liver tests should be considered and their role clarified before DILI is assumed to be the cause of liver injury.

A detailed history, including relevant information such as review of ethanol consumption, concomitant medications, herbal remedies, supplement consumption, history of any pre-existing liver conditions or risk factors, should be collected.

Laboratory tests should include ALT, AST, total bilirubin, direct and indirect bilirubin, Gamma-glutamyl transferase (GGT), prothrombin time (PT)/International Normalized Ratio (INR), alkaline phosphatase, albumin, and creatine kinase. If available, testing of Glutamate Dehydrogenase (GLDH) is additionally recommended.

Perform relevant examinations (Ultrasound or Magnetic resonance imaging (MRI), Endoscopic retrograde cholangiopancreatography (ERCP)) as appropriate, to rule-out an extrahepatic cause of cholestasis. Cholestasis (is defined as an Alkaline Phosphatase (ALP) elevation $> 2.0 \times$ ULN with R value < 2 in participants without bone metastasis, or elevation of the liver-specific ALP isoenzyme in participants with bone metastasis).

Note: The R value is calculated by dividing the ALT by the ALP, using multiples of the ULN for both values. It denotes whether the relative pattern of ALT and/or ALP elevation is due to cholestatic ($R \leq 2$), hepatocellular ($R \geq 5$), or mixed ($R > 2$ and < 5) liver injury. In clinical situations where it is suspected that ALP elevations are from an extrahepatic source, the GGT can be used if available. GGT may be less specific than ALP as a marker of cholestatic injury, since GGT can also be elevated by enzyme induction or by ethanol consumption. It is more sensitive than ALP for detecting bile duct injury.

Table 6-3 provides guidance on specific clinical and diagnostic assessments which can be performed to rule-out possible alternative causes of observed Liver function test (LFT) abnormalities.

Table 6-3 Guidance on clinical and diagnostic assessments to rule out alternative causes of observed LFT abnormalities

Disease	Assessment
Hepatitis A, B, C, E	
 IgM anti-Hepatitis A Virus (HAV); Hepatitis B virus surface antigen (HBsAg), IgM & IgG anti-HBc, Hepatitis B Virus (HBV) Deoxyribonucleic acid (DNA); anti-Hepatitis C Virus (HCV), HCV RNA, IgM & IgG anti-Hepatitis E Virus (HEV), HEV RNA
Cytomegalovirus (CMV), Herpes simplex virus (HSV), Epstein-Barr virus (EBV) infection	
 IgM & IgG anti-CMV, IgM & IgG anti-HSV; IgM & IgG anti-EBV
Autoimmune hepatitis	
 Antinuclear Antibodies (ANA) & Anti-Smooth Muscle Antibody (ASMA) titers, total IgM, IgG, IgE, IgA
Alcoholic hepatitis	
 Ethanol history, GGT, Mean Corpuscular Volume (MCV), CD-transferrin
Nonalcoholic steatohepatitis	
 Ultrasound or MRI
Hypoxic/ischemic hepatopathy	
 Medical history: acute or chronic congestive heart failure, hypotension, hypoxia, hepatic venous occlusion. Ultrasound or MRI.
Biliary tract disease	
 Ultrasound or MRI, ERCP as appropriate.
Wilson disease (if <40 yrs old)	
 Caeruloplasmin
Hemochromatosis	
 Ferritin, transferrin
Alpha-1-antitrypsin deficiency	
 Alpha-1-antitrypsin

Other causes should also be considered based upon participants' medical history (hyperthyroidism / thyrotoxic hepatitis – T3, T4, TSH; cardiovascular disease / ischemic hepatitis – ECG, prior hypotensive episodes; Type 1 diabetes mellitus / glycogenic hepatitis).

Following appropriate causality assessments, as outlined above, the causality of the treatment is estimated as "probable" (i.e. $>50\%$ likely), if it appears greater than all other possible causes

of liver injury combined. The term “treatment-induced” indicates probably caused by the treatment, not by something else, and only such a case can be considered a DILI case and should be reported as an SAE.

All cases confirmed on repeat testing meeting the laboratory criteria defined above, with no other alternative cause for LFT abnormalities identified, should be considered as “medically significant” and thus, meet the definition of SAE and should be reported as a SAE using the term “potential treatment-induced liver injury.” All events should be followed up with the outcome clearly documented.

